3.9 Reference to the IFU

An IFU leaflet is included in each secondary packaging: on one face, the IFU of Healsea® Babykids, on the other face, the IFU of Healsea® Placebo (See appendix A).

4. Justification for the design of the clinical investigation

The common cold is the most frequent upper respiratory tract infection (URTI), which is the most commonly treated acute problem in primary pediatric care (1). The common cold is an acute viral infection of the upper respiratory tract, involving, to variable degrees, sneezing, nasal congestion and discharge (rhinorrhea), sore throat, cough, low-grade fever, headache, and malaise (2). The common cold is caused by a variety of viruses. Improvements in viral detection techniques during the past two decades, including various viral antigen detection methods and particularly the advent of PCR-based assays, have substantially increased the rates of viral detection in clinical specimens. The relative proportions of different viruses in the cause of the common cold vary depending on several factors, such as age, season, and viral sampling and detection methods. However, rhinoviruses have been consistently found to be the most common cause in all age groups, irrespective of the viral detection techniques used. Yearly, rhinoviruses account for about 30–50% of all respiratory illnesses, but during the autumn peak season these viruses can cause up to 80% of all upper respiratory infections. Coronaviruses and Influenza viruses account for about 10-15% and for 5-15% of acute infectious rhinitis respectively. Other viruses such as Respiratory Syncytial virus, Adenoviruses and Parainfluenza viruses are less involved (2).

Acute viral rhinitis is generally self-limiting. In children where the illness is not self-limiting and extends beyond 7-10 days, many agree that a bacterial infection is likely (2,3). Acute bacterial rhinosinusitis is diagnosed in a child based on several criteria: persistent upper respiratory tract symptoms more than

10 days (cough or nasal discharge or both); or recurrence of symptoms after initial improvement: fever, worsening cough, or worsening or new purulent rhinorrhea; or severe onset of symptoms like fever or purulent nasal discharge lasting more than three consecutive days associated with facial tenderness or headache. Bacterial over infections and progression to a chronic condition are favoured by the formation of biofilms, which facilitate bacterial growth and persistence as well as reducing antibiotic efficacy (4,5). Despite the usually benign nature of the illness, the socioeconomic impact of acute rhinitis is well established: visits to GP, additional prescriptions and over prescription of antibiotics, absence from work, school or day care (1).

Although clinical evidence from well-designed trials is scarce (6), European and American guidelines for acute rhinosinusitis recommend daily nasal saline irrigation for reduction of the severity of symptoms and for speeding recovery (2,7). The exact mechanisms by which nasal irrigation works are not fully elucidated. However, most of the experts agree that it is primarily a mechanical intervention leading to direct cleansing of the nasal mucosa (8,9). The mucus lining the nasal cavity may be softened and dislodged. The increase of mucociliary clearance is associated with a decrease of pathogens burden. Moreover, inflammatory mediators such as cytokines, prostaglandins and leukotrienes can be removed, favoring the resolution of URTIs. Although the impact of the salt concentration of the saline solution on all these parameters is still debated, the efficacy of saline irrigation remains moderate (6).

The Healsea® products are a saline-based nasal spray line supplemented with a natural Symbiofilm[™] extract (0.02% to 0.04%) isolated from the marine flora of the deep seas of the Panarea Islands, in Sicily. Healsea® Babykids is an isotonic saline solution (0.9%) with Symbiofilm[™] (0.04%).

Symbiofilm[™] is an exopolysaccharide composition secreted by *Bacilllus licheniformis* LP-T14, a Lallemand Pharma proprietary strain, with *in vitro* antibiofilm activity and detachment properties against various bacterial pathogens involved in respiratory tract infections, i.e *Haemophilus influenzae type b, Klebsiella pneumoniae, Pseudomonas aeruginosa, Staphylococcus aureus and streptococcus pneumoniae*. Antibiofilm effects of Symbiofilm[™] have been reported *in vitro*, using microtiter plate-based model and human nasal epithelial cells. The antibiofilm activity of Symbiofilm[™] is likely to rely on its emulsifying properties. Symbiofilm[™] (400 µg/ml) has also been demonstrated to protect *in vitro* human nasal epithelial cells viability after Adenovirus, Rhinovirus, Coronavirus OC43 and Flu infections.

The technical performances of Symbiofilm ™ may enhance the benefit of saline nasal irrigation for the treatment of acute infectious rhinitis and common cold.

The aim of this investigation is to demonstrate that thanks to the antibiofilm and antiviral properties of Symbiofilm $^{\text{\tiny TM}}$, isotonic saline solution and Symbiofilm $^{\text{\tiny TM}}$ alleviate symptoms of the acute rhinitis phase with better efficacy than isotonic saline solution without Symbiofilm $^{\text{\tiny TM}}$.

To demonstrate the efficacy of Healsea® Babykids in common cold, a Double Blind Randomized Controlled Study will be performed. The efficacy of the test product will be assessed by comparison with an isotonic saline nasal spray.

5. Risks and Benefits of the Investigational Device and Clinical Investigation

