7.4 Procedures

7.4.1 Description of clinical investigation-related procedures

The clinical investigation is divided into 2 parts:

- Part 1 (D1-D11): treatment of the acute phase with Healsea® Babykids/Placebo, with a minimum of 7-day-treatment period (14 intakes of investigational device) up to 10 days (20 intakes of investigational device).
- Part 2 (up to D15/D18): follow-up phase.

The clinical investigation comprises 2 visits.

Visit 1 (V1) - (Day 1): Screening/Inclusion/Randomization

Parents/legal guardians of children with symptoms of acute infectious rhinitis for ≤48h will go to the site for the screening/inclusion visit (visit 1). The investigator will give oral information relative to the study and will answer all questions relative to the study participation. Appropriate information using drawings will be also delivered to the child. If both parents/legal guardians agree that their child participate in the study, they will receive the information sheet and will be also asked to give a written consent. In case one parent should not be available for the visit; he/she will be asked to confirm in writing that he/she agrees with the participation of the child in the study. Each screened subject will be assigned a subject identifier number during screening that will be used on all subject documentation. The subject identifier number will contain the site number and the subject number and will be assigned in numerical order at the screening visit based on chronological order of screening dates (e.g., 01-010 for the 10th subject screened at the Site #01).

The investigator or his/her delegated designee will:

- Record demographic data, medical history and ongoing medication.
- Perform a physical and clinical examination.
- Instruct the parents/legal guardian of the patient to complete the baseline ARSSQ questionnaire, The investigator/designee will then rate patient nasal congestion symptoms and additional signs of acute rhinitis (runny nose, nasal crust, sneezing, cough)

Version 1.1 –2023.02.02 Page **36** of **64**

- Verify that eligibility criteria are fulfilled.
- Explain to the parents/legal guardians how to complete every day the paper diary ARSSQ recording, how to report concomitant medications, adverse events/incidents.
- Remind the parents/legal guardians to return the device for assessment of compliance to the treatment at V2 and to bring back the paper diary at the study end.

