The investigator will provide the parents/legal guardians with the device according to the site specific treatment list, in order to respect the 1:1 randomization (blocks of 4). The investigator will explain how to use it.

NB: The first use of the device will be performed in the evening of the Day 1.

D1-D8 up to -D11 (at home):

The Parent/legal guardian will be asked to complete the ARSSQ in the diary, once daily in the evening. The symptoms occurring from the morning to the evening should be taken into consideration. The ARSSQ shall be scored at least from D1 to D8. Adverse events/incidents and concomitant medications are to be reported during the whole period

Between D8 and D11 (at home):

End of Healsea® Babykids/Placebo nasal spray.

➤ NB: The last study nasal spray intake will be performed **between D8 and D11** in the morning. The patient should stop taking the investigational device before D11 only if the question 1 "not sick" of the ARSSQ is ticked YES for 2 consecutive days.

Up to D15/D18 (at home):

Parents/legal guardians will continue to complete the paper diary daily (incidents/adverse events/expected undesirable sides effects, concomitant medications). For patients for whom common cold symptoms persist, parents/ legal guardians will be instructed to continue to complete the ARSSQ, until the subject feels not sick for two consecutive days.

Visit 2 (V2) - (Day 15-Day 18): end of study

The investigator or his/her delegated designee will:

- Perform a physical and clinical examination.
- Collect the patient diary.
- Review the paper diary to validate adverse events pertinent in the context of the common cold, incidents linked to medical device use and concomitant medications reported by the parents/legal guardians. Complete the e-CRF accordingly and report any new relevant safety events
- Ask parents/legal guardians to complete the ARSSQ if the patient still has symptoms.
- Assess the compliance to the treatment by weighing the device bottle returned by the parents/legal guardians. If a nasal spray is not returned or lost, the investigator will ask the

Version 1.1 –2023.02.02 Page **37** of **64**

Study Number: LPH-2202

parents/legal guardians to specify the number of missed nasal spray uses and will report the data into the e-CRF.

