The device accountability will be performed all over the study according to the SOP "Investigational Product Management" of the CRO. Briefly, sites will complete an accountability log after each receipt of the Medical Device and dispensation to parents/legal guardians. The CRA in charge of the site

monitoring will check the accountability log at each visit. At V2, the compliance will be assessed by weighing the device brought back by the parents/legal guardians.

Return of unused or expired investigational devices to the sponsor will be tracked using a specific record.

13. Ethical consideration

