Appendix A: IFU

HEALSEA®BABYKIDS

[figure not shown]

INDICATION	UNDESIRABLE EFFECTS.		
Healsea® babykids is a nasal spray indicated in	In case of undesirable effects, contact your doctor.		
children above 2 years to clean and moisten the nose			
during colds and rhinitis			
COMPOSITION	STORAGE AND WASTE RECOMMENDATION		
Isotonic saline solution (salinity 0.9%),	Store at room temperature and not above 30°C.		
Symbiofilm®.	See the expiry date on the box or the bottle.		
	Ask your pharmacist to throw out the bottle after use.		
	These measures contribute to protect the		
	environment.		
DIRECTION OF USE	TECHNOLOGY		
Healsea® BABYKIDS shall be administered in children	The spray pump APF (Advanced Preservative Free)		
with the help of an adult.	uses a technology that permits to dispense a		
One-two sprays twice a day in each nostril for 10 days	preservative free solution.		
or as recommended by your doctor or pharmacist.			
PRECAUTION OF USE	HOW TO USE HEALSEA® BABYKIDS?		
- Keep out of reach of children.	1. Place the nozzle smoothly into the nostril while		
-If symptoms persist more than 10 days, ask for	keeping head straight.		
advices to your doctor or pharmacist.	2. Once the nozzle is placed, press on the nozzle in		
-The bottle shall be used by only one person for	each nostril. Let flow the excess of solution and		
hygiene reason and to avoid the transmission of	wipe.		
pathogenic agents that could be in contact with the	3. Clean the nozzle with tissue, soapy water, rinse		
nozzle.	and dry after every use.		
CONTRAINDICATION			
Do not use in children and adolescents under 2			
years.			
Do not use in case of hypersensitivity or allergy to one			
or several components.			

Healsea® BABYKIDS is a nasal spray containing isotonic saline solution mixed with an innovative extract, Symbiofilm®, isolated from the marine biosphere.

Healsea® BABYKIDS is a natural care preservative free allowing to clean and moisten the nasal mucosa. Symbiofilm® is a marine postbiotic, which contains exopolymeric substances, that enhances mechanically the cleansing efficiency of isotonic water.

Symbiofilm® reduces the development of biofilm from respiratory pathogenic microorganisms by mechanical action as well as the mucosal adhesion and helps reducing the spreading of viruses in-vitro. Healsea® BABYKIDS is the ideal solution for children who suffer from colds or rhinitis by cleaning the nasal cavity and eliminating allergens and infectious agents.

Date: Switzerland

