9. COMPLIANCE

Compliance will be calculated according to the following formula and analysed on the Safety set, by treatment group and overall.

The compliance will be calculated as follows:

Compliance (%) = [Initial weight of the container (g) – Real weight of the container at the end of the study (g)] \times 100 / [Initial weight of the container (g) – Theoretical weight of the container at the end of complete study (g)]

with:

- Initial weight of the container = 32.615 g;
- Theoretical weight of the container at the end of complete study is a function of treatment duration and is noted *weight*_{theo};

i.e.:

Compliance (%) =
$$100 \times \frac{32.615 - weight_{end}}{32.615 - weight_{theo}}$$

with weightend the real weight of the container at the end of the study in g.

The table below gives the value of $weight_{theo}$ by last day of treatment:

Table 1: Theoretical weight of the container at the end of complete study by last day of treatment

Patient stopped treatment	weighttheo (g)
Before D8	27.55875
At D8 morning	27.55875
At D8 evening	27.21750
At D9 morning	26.85750
At D9 evening	26.53750
At D10 morning	26.21500
At D10 evening	25.87125
At D11 morning	25.52500
At D11 evening	25.20250
At D12 morning	24.86500
At D12 evening	24.51000
After D12	24.51000

Compliance will be also described according to the following categories: <80%, [80%; 120%] and >120%.

Note that in case of spray not returned, compliance will be considered unknown and missing.

AXIODIS CRO 16/47

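### The leaflet in every study box tells families to discard the bottle that must be weighed at Visit 2, and the SAP does not use the protocol's fallback for unreturned bottles (low impact)

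*Protocol*

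**What the plan says.** **Leaflet.** Protocol sections 3.8 and 3.9 put a two-faced leaflet in every study box: "An IFU leaflet is included in each secondary packaging". In Appendix A, the storage and waste entry on the Healsea Babykids face and on the Placebo face is the same: "Ask your pharmacist to throw out the bottle after use".

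**Return and weighing.** Among the Visit 1 tasks in Protocol section 7.4.1 is: "Remind the parents/legal guardians to return the device for assessment of compliance to the treatment at V2". The Visit 2 tasks include: "Assess the compliance to the treatment by weighing the device bottle returned by the parents/legal guardians". Protocol section 12 (Device accountability) repeats this: "At V2, the compliance will be assessed by weighing the device brought back by the parents/legal guardians".

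**Unreturned bottle.** Section 7.4.1 goes on: "If a nasal spray is not returned or lost, the investigator will ask the" parents how many uses were missed, and the answer is entered in the e-CRF. SAP section 9 takes a different line: "Note that in case of spray not returned, compliance will be considered unknown and missing".

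**Use of compliance.** Protocol section 11 and SAP section 7.2 make compliance below 80% or above 120% a major deviation. SAP section 5 defines the Per Protocol (PP) Set as the Full Analysis Set (FAS) without major deviations. It runs the primary and secondary analyses on the FAS and calls the PP analyses supportive.

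**The concern.** The study's own written material tells families to dispose of the object that the protocol needs back. The leaflet stays in the home, while the reminder to return the device is given on D1, at least a week before the bottle is finished with. The compensation in Protocol section 7.3.9 depends on diary completion and attending visits; it does not mention the bottle.

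A discarded bottle has no end weight, and the SAP compliance formula depends on that weight. What is at stake is the completeness of the compliance table and the ability to apply the compliance criterion for the PP Set. The fallback in section 7.4.1 would recover part of this, but the SAP gives it no role.

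**Working it through.** **1. Planned size.** The one planning figure used below is 200 children (Protocol section 6.4, SAP section 4). It is consistent with its stated basis. For a standardised difference of 0.4, two-sided 5% and 80% power, n = 2 × (1.960 + 0.842)² / 0.4² = 98.1, so 99 per arm. The t-test version gives 99.1, rounded up to 100, and power at 100 per arm is 80.4%. Nothing below depends on this calculation beyond the total of 200.

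**2. Time the finished bottle is at home** (Protocol section 7.4.1: last spray D8 to D11, Visit 2 D15 to D18).
- Shortest: 15 − 11 = 4 days.
- Longest: 18 − 8 = 10 days.

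**3. What the SAP formula needs.** Compliance (%) = 100 × (32.615 − end weight) / (32.615 − theoretical weight). From SAP Table 1 the denominator is:
- last use D8 morning: 32.615 − 27.55875 = 5.05625 g;
- last use D11 morning: 32.615 − 25.525 = 7.090 g.

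Without the bottle there is no end weight and the ratio cannot be computed. The SAP accordingly sets it to missing.

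**4. The instructions side by side.**

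| Place | Instruction or rule |
|---|---|
| Leaflet, both faces | dispose of the bottle through a pharmacist |
| Protocol 7.4.1, Visit 1 | remind parents to bring it back |
| Protocol 7.4.1, Visit 2, and section 12 | weigh it |
| Protocol 7.4.1, bottle missing | record parent-reported missed uses |
| SAP 9, bottle missing | compliance missing |

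The first row conflicts with the next two, and the fourth conflicts with the fifth. Nothing in the text supplied says that the leaflet line is removed or overridden for the study.

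**5. Size.** The documents give no non-return rate. As an assumption, of 200 children:
- 5%: 200 × 0.05 = 10 without a weighed value;
- 10%: 20;
- 20%: 40.

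These are counts for any cause of non-return. No figure in the documents says what share the leaflet would cause.

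**6. What the fallback could recover.** A missed-use count m out of k planned intakes gives 100 × (k − m) / k.
- k = 14 (D8 morning): m = 2 gives 85.7%, m = 3 gives 78.6%.
- k = 20 (D11 morning): m = 4 gives 80%, m = 5 gives 75%.

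So the reported count can place a child below 80%. It cannot show use above 120%, because it never exceeds 100%.

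**The case against.** The strongest reply is that the protocol foresees unreturned bottles. It reminds parents at Visit 1 and collects missed uses if the bottle does not come back, so a lost bottle costs the weight but not all compliance information. That stands. The remaining gap at analysis comes from the SAP ignoring those data.

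The bottle is also far from empty: 20 intakes × 4 puffs × 0.1 mL = 8 mL of 20 mL, so a family may see no reason to discard it promptly. That stands too, and is one reason not to assume a high non-return rate.

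Some stronger readings are tempting, and the documents do not support them:

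- *A child without a weight stays in the PP Set by default.* Missing compliance is not on the list of deviations, so a literal reading points that way. But SAP sections 5 and 7.2 have deviation status validated at the data review meeting, and Protocol section 9.3 requires evaluability decisions to be documented for each subject before lock. SAP section 7.2 also has rules based on intake counts that need no weight. The plan leaves the outcome open.
- *The Visit 1 reminder is the only counter-instruction.* This cannot be known. The parents' information sheet is not in the text supplied, the diary is shown only in part, and the label wording in Protocol section 3.7.3 is broken by extraction.
- *A particular number of children will be misclassified.* That would multiply two rates, non-return and true non-compliance, neither of which is in the documents.
- *Accountability is lost.* Section 12 keeps receipt and dispensation logs whether or not the used bottle returns.

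**Conclusion.** The contradiction is real and can be read directly from the documents: the leaflet says dispose, while the procedures say return and weigh. A family that follows the leaflet in the 4 to 10 days before Visit 2 has no weighed compliance. The protocol then collects missed uses, but SAP section 9 makes no use of them, so the 80% to 120% criterion cannot be applied from weight and PP status falls to the data review.

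The impact is low. It reaches the compliance table and the supportive PP analyses only. The disposal line is identical on both leaflet faces, so no difference between arms is expected from it. The primary test is on the FAS, which does not depend on compliance. The range of 10 to 40 of 200 children rests wholly on an assumed 5% to 20% non-return. The conflict between the texts does not depend on that assumption.

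**What to change.** 1. **Labels and leaflet.** Add to the study box and bottle labels: *Keep the bottle after the last use and bring it to Visit 2.* Replace or override the disposal line on both leaflet faces with the same message. Keep the Visit 1 reminder.
2. **SAP section 9.** Reconcile it with Protocol section 7.4.1. When the bottle is not returned, derive compliance from the parent-reported missed uses and flag it as reported rather than weighed. State that this source cannot detect use above 120%, and say how a child with neither source is classified for the PP Set.

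**Cost.** The packaging and labels are already specific to this trial, so the first item is a small wording change with the usual notification and no extra visits, staff or patients. The second uses data that the e-CRF already collects. On timing, the SAP is dated August 2023, while the protocol planned a February 2023 start and four months in all. If supplies had already been used by then, the label change would serve only further use of this material, and the SAP rule would need to be settled before unblinding.

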5.1 Anticipated clinical benefit

Healsea® Babykids is an isotonic saline solution (0.9%) with Symbiofilm™ (0.04%).

Healsea® Babykids is indicated in children above 2 years to clean and moisten the nose during colds and rhinitis.

The exact mechanisms by which classic saline nasal irrigation works are not known. However, most of the experts agree that it is primarily a mechanical intervention leading to direct cleaning of the nasal mucosa.

The supplementation of the saline solution with Symbiofilm[™] impacts the performance of the device. Indeed, Symbiofilm[™] has also been demonstrated to protect in vitro human nasal epithelial cells viability after Adenovirus, Rhinovirus, Coronavirus OC43 and Flu infection.

Therefore, isotonic saline solution and Symbiofilm[™] may act in a synergistic manner to alleviate symptoms of the acute rhinitis phase resulting in better efficacy than isotonic saline solution without Symbiofilm[™] used as Placebo. As a consequence, patients receiving daily administrations of **Healsea® Babykids** are expected to recover more rapidly from common cold than those receiving the Placebo.

Subjects who receive Placebo will not benefit from as effective a treatment although nasal administrations of isotonic saline are well described as cleansing and hydrating the nasal mucosa. Nevertheless, these subjects will receive all concomitant treatments necessary in the context of acute rhinitis with the exception of other saline solutions.

